### **3. Study Endpoints/Events/Outcomes**

1. Primary Endpoint/Event/Outcome: In a double-blind randomized design, 100 abstinent (~2 weeks abstinent) individuals with alcohol use disorder (AUD) recruited from Lodging Plus Program will receive 10 sessions (2 sessions per day for 5 days) of either (i) transcranial direct current stimulation (tDCS) to the PFC or (ii) sham-tDCS. All subjects will perform the reversal learning task during tDCS intervention (active or sham) to prime the engagement of the NAcc-PFC brain circuit that mediates cognitive flexibility. Rest fMRI and craving measures will be collected before the first and after the last day of tDCS sessions, and about one month after the last fMRI (timepoint depending on participant availability). Monthly follow-up interviews will be conducted for approximately 8 months after intervention completion to query relapse status. Dependent variables will be (i) change in NAcc-PFC FC between 2,3 weeks of abstinence and one month later, (ii) change in craving scores between 2 and 3 weeks of abstinence and (iii) relapse status ~8 months after study participation. Aim 1: To investigate whether NAcc-PFC FC can be modulated, we will compare magnitude and durability of change in NAcc-PFC FC between active-tDCS and sham-tDCS groups. Aim 2: To determine if PFC stimulation has a short-term effect on behavior related to clinical outcome, we will compare change in craving scores (difference in craving scores between 2 and 3 weeks of abstinence) between active-tDCS and sham-

tDCS groups. Aim 3: To correlate neuromodulation intervention with long-term clinical outcome, we will record craving and relapse status during the ~8 months following treatment discharge. We will examine the relationship between change in NAcc-PFC FC between 2 and 3 weeks of abstinence and subsequent (i) monthly craving scores and (ii) relapse status. Aim 4: Examine relationships between genetic variants, epigenetic changes and treatment outcome (e.g. durability, functional connectivity).

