#### 4. Study Intervention(s)/Investigational Agent(s)

1. Description: As in previous clinical studies that achieved treatment response and reduction of relapse probability (Klauss et al. 2014), patients will receive two 13 minute daily sessions with a rest interval (no stimulation) of 20 minutes in between (13:20:13 schedule; as in (Klauss et al. 2014; Monte-Silva et al. 2013)) of either active (2-mA) or sham transcranial direct current stimulation (tDCS) every day for five consecutive days. This study will add to the literature by having patients practice the reversal learning task (D'Cruz et al. 2011) during tDCS intervention, to enhance paired neuromodulation. While patients practice the reversal learning task, half of the patients will receive active tDCS stimulation to the left DLPFC to enhance top-down control and improve the tuning or gating of the extraneous information and the other half will receive sham tDCS.
2. The tDCS will be performed with Neuroelectrics Starstim Enobio 20 (Neuroelectrics Barcelona, Spain). This device has been approved for use in research without an investigational device exemption due to meeting criteria for non-significant risk. In addition, the device has built in safety mechanisms which allow for the immediate cessation of stimulation should the subject become uncomfortable or impedance levels too high. The current will be administered via two saline soaked electrode sponges (approximately 25cm^2) for two 13 minute blocks. The current strength during each administration will be 2 mA. These administration procedures are in line with other protocols that have outlined safe administration (Nitsche et al. 2008, 2007). Across more than 2000 subjects no side-effects have been reported with the exception of slight itching under the electrode and occasional occurrence of headache, fatigue, or nausea (Poreisz et al. 2007). The anodal electrode will be placed over left DLPFC and the cathodal electrode will be placed over right DLPFC.
3. Drug/Device Handling: We will use transcranial direct current stimulation (tDCS) to stimulate dorsolateral prefrontal cortex (DLPFC). TDCS is a non-

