abstinence) between active-tDCS and sham-tDCS groups. Aim 3: To correlate neuromodulation intervention with long-term clinical outcome, we will record monthly craving and relapse status ~8 months after intervention completion. We will examine the relationship between change in NAcc-DLPFC FC between 2 and 3 weeks of abstinence and subsequent (i) monthly craving scores and (ii) relapse status. Patients will be asked to complete these scales monthly for ~8 months after intervention completion to examine long-term effects. Patients will be asked to come back for 3 in-person (or remote) visits scheduled approximately 1, 4 and 8 months later, with the actual date of each visit varying depending on participant availability. On a case-by-case basis, follow-ups may be scheduled up to 3 months after each timepoint (1, 4, and 8 month timepoints) depending on participant availability. In these in-person (or remote) visits the participants will complete the same assessments and fill out questionnaires assessing behavior, personality and substance use metrics as in the baseline appointment. At the ~1-month follow-up timepoint, the participant will also complete a third MRI session, which could be on the same day of the assessments and questionnaires or on a different day, depending on participant availability.

2. Study Procedures: Randomization: Participants will be randomly assigned to either active or sham tDCS. Blinding: Participants will not be informed on their assigned protocol. During consent, they will be informed that there is a 50% chance of receiving active tDCS or sham tDCS every day for five consecutive days. Study appointments will be conducted either in-person, or remotely.

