3. Participants who consent to the study and meet study criteria as per the screening evaluation will be asked to participate in an 8-day session study, be available for monthly phone follow-up measures after study completion to query relapse status and for 3 in-person (or remote) follow-up visits. At any of the in-person follow-up visits, research staff may test participants for recent alcohol use using a Breathalyzer (will not be administered if assessments are remote). Participants will be informed of alcohol level, but will not be excluded from the study if test shows recent alcohol use. If Breathalyzer shows alcohol level of > 0.08%, participant will be asked to reschedule visit. While the target will be to conduct follow-up phone calls every month, plus in-person/remote assessments at 1, 4 and 8 months

timepoints, the actual date for these follow-up sessions will vary depending on participant availability.

The participants who are referred to our study by the Consortium of Addiction Research (CAR; approved under IRB protocol #STUDY00005170) will be asked if they are interested in participating. Participants will be informed about the study via the “1406M51241 Invite,” which informs them that they need to be available for 8 appointments during their stay at the treatment program. They also need to be available for monthly (depending on subject availability) phone follow-up measures after study completion to query relapse status and for the 3 in-person (or remote) follow-up visits.

**Baseline Interview:** A research staff member will meet the participant either in person or through a virtual video conference to complete the informed consent process with the participant and administer surveys assessing behavior, personality and substance use, and alcohol craving levels. Understanding of informed consent will be assessed with the “Assessment of Informed Consent” form. Participants will also complete a screening questionnaire for contraindications of MRI scanning. Females who could potentially be pregnant will be tested for pregnancy and, if positive, will not be allowed to participate. If testing is refused, participation will not be allowed. Baseline assessments will take about 1.5 hours total.

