## **16. Data Management**

1. Data Analysis Plan: A mixed model analysis of variance will be conducted with between-group measures (sham vs active tDCS) and within-group measures (FC and craving reports before and after cognitive flexibility training and tDCS intervention). This mixed model analysis will examine main effects and interaction effects. To examine the long-term effects of cognitive flexibility training and tDCS, we will conduct a repeated measures analysis using longitudinal data collected monthly for 6 months after intervention completion. A Log-rank (Mantel-Cox) Test (used in Klaus et al 2014) will be conducted to establish the efficacy of cognitive flexibility training and active tDCS vs. cognitive flexibility training and sham tDCS in the time domain.
2. Power Analysis: The study in reference is a pilot study for which a power analysis is not applicable.
3. Data Integrity: The principal investigator and co-investigator will monitor data quality for this study. They will ensure that data are generated, documented (recorded), and reported, in compliance with this protocol, with Good Clinical Practice, and any other applicable regulatory requirements.

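### The long-term repeated-measures analysis states no baseline term; if applied to monthly craving by arm, omitting pre-tDCS craving gives up precision

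*Combined protocol and SAP*

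**What the plan says.** Section 16 (Data Management, Data Analysis Plan) lists three analyses.

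- **Short term:** a mixed-model analysis of variance with arm as the between-group factor and "within-group measures (FC and craving reports before and after cognitive flexibility training and tDCS intervention" as the repeated part. The pre-intervention craving score is used here.
- **Long term:** a separate sentence says "we will conduct a repeated measures analysis using longitudinal data collected monthly for 6 months after intervention completion". It names no outcome, arm factor, covariate or change score.
- **Time domain:** a log-rank test of training with active tDCS against training with sham.

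On data collection, Section 3 states "Rest fMRI and craving measures will be collected before the first and after the last day of tDCS sessions". The Baseline Interview in Procedures Involved has staff "administer surveys assessing behavior, personality and substance use, and alcohol craving levels". For follow-up, Procedures Involved states "Patients will be asked to complete these scales monthly for ~8 months after intervention completion to examine long-term effects", and Aim 3 in Section 3 says "we will record craving and relapse status during the ~8 months following treatment discharge".

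On allocation, Procedures Involved says only "Participants will be randomly assigned to either active or sham tDCS", with no mention of stratification. Section 4 implies a 1:1 split ("half of the patients will receive active tDCS stimulation to the left DLPFC").

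**The concern.** The long-term sentence has its own data set, which begins after treatment, and no other section supplies a baseline term for it. Read as an arm comparison of monthly craving, it compares post-treatment levels only. Averaging over months reduces visit-to-visit noise but does not remove stable differences between people, and these remain in the error for the averaged arm effect. A pre-randomised-treatment score on the same scale is the natural variable to remove part of that variation, and the trial already schedules it for everyone.

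At stake is the precision of the long-term craving contrast in a trial with about 35 completers per arm. There is also a secondary effect: nothing described in the allocation balances baseline craving, so part of any chance difference between arms will show in the unadjusted follow-up means.

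**Working it through.** **The plan's own figures.** There is no power, SD, effect size or correlation to reproduce; Section 16 says a power analysis does not apply to this pilot. The only sample-size arithmetic is in Section 25: 100 consented, 25% attrition, 70 complete. It does not reproduce exactly (100 × 0.75 = 75; 70 / 0.75 = 93.3, so 94; the pair 100 and 70 fits 30%). That mismatch is a separate matter. I use 70 / 2 = 35 per arm.

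**Assumed inputs.** Six monthly values, two-sided 5%, effect d in single-visit SD units (0.4 and 0.5), correlation rm between any two months, and correlation rb between pre-tDCS craving and each month.

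**Variance of a person's six-month mean (single-visit SD = 1).**
- Unadjusted: V = (1 + 5 rm) / 6, which is 0.583 at rm = 0.5, 0.667 at 0.6 and 0.750 at 0.7.
- Adjusted for baseline: V − rb². The proportional cut is rb² / V.

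**Power.** Noncentral t with noncentrality d / √(2V/35) and 68 degrees of freedom. With adjustment, V is replaced by (V − rb²)(1 + 1/66), with 67 degrees of freedom.

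| rm | rb | Variance cut | Power, d = 0.4 | Power, d = 0.5 |
|---|---|---|---|---|
| 0.5 | 0 | 0% | 57.9% to 57.3% | 77.0% to 76.4% |
| 0.6 | 0.2 | 6% | 52.4% to 54.3% | 71.4% to 73.4% |
| 0.5 | 0.3 | 15% | 57.9% to 64.5% | 77.0% to 83.0% |
| 0.6 | 0.3 | 13.5% | 52.4% to 57.8% | 71.4% to 76.9% |
| 0.7 | 0.3 | 12% | 47.8% to 52.2% | 66.3% to 71.2% |
| 0.5 | 0.5 | 43% | 57.9% to 80.9% | 77.0% to 94.3% |

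The gain at rb = 0.3 runs from 4.4 points (rm = 0.7, d = 0.4) to about 6.6 points (rm = 0.5, d = 0.4), so it does not reach 5 points in every case.

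A simulation of 5,000 trials at rm = rb = 0.5 and d = 0.5 gave 76.8% unadjusted and 94.5% adjusted, in line with the last row. With eight monthly values instead of six the variance cuts hardly move: 44.4% against 42.9% at rm = rb = 0.5, and 13.8% against 13.5% at rm = 0.6, rb = 0.3.

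**Chance imbalance.** The standard error of the baseline difference between arms is √(2/35) = 0.24 SD. Only the fraction rb of it passes into follow-up: 0.3 × 0.239 = 0.07 SD at rb = 0.3, and 0.5 × 0.239 = 0.12 SD at rb = 0.5.

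**The case against.** **The analysis is inferred.** The sentence names neither craving nor arm. In Procedures Involved the 6-month window belongs to relapse queries, while monthly craving is set for about 8 months. Aim 3 relates monthly craving to change in connectivity, not to arm. This stands, and the point is therefore conditional. The inference is still reasonable: the sentence concerns long-term effects of training and tDCS, both arms receive the training, and the scales are repeated monthly to study long-term effects.

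**A reader might infer that the plan rules baseline out, or that the unadjusted comparison is biased.** The documents support neither. A baseline term is unstated, not prohibited. Participants are randomised, so the unadjusted comparison is unbiased with correct type I error, and its standard error already allows for chance imbalance. Nor does a baseline difference carry over in full; only the fraction rb does.

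**Stable differences do not affect every term.** In a repeated-measures model they drop out of the month and arm-by-month terms. This also stands; the loss concerns the arm effect averaged over months, and the plan does not say which term is the test.

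**The gain may be small.** Baseline craving is measured at about two weeks of abstinence in a supervised residential programme, and follow-up is largely after discharge, so a low correlation is plausible. At rb = 0.2 the gain is about 2 points. Six complete monthly values is also optimistic, since contact dates depend on availability.

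**It is a pilot.** That explains the absence of a power target. It gives no reason to leave out a score already collected.

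**Conclusion.** The point holds as one of precision. Section 16 states no baseline term for the long-term repeated-measures analysis. Where that analysis is applied to monthly craving by arm, omitting pre-tDCS craving makes the averaged arm effect less precise than the collected data allow.

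The size depends wholly on assumed correlations and effects. It runs from a loss of under 1 point of power when baseline is uninformative to a gain of 17 to 23 points when both correlations are 0.5. At the low correlations that a residential baseline may well have (0.2 to 0.3), the gain is about 2 to 7 points. The trade-off favours adjustment because the worst case is so small.

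The short-term craving comparison under Aim 2 already uses the pre-intervention score and is not affected. Connectivity under Aim 1 and the log-rank test are outside this point.

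**What to change.** In Section 16, Data Analysis Plan, name the outcome and the model. Suggested text: *Monthly craving will be analysed in a repeated-measures model with arm, month, arm-by-month, and craving measured before the first tDCS session, with its interaction with month, as covariates. The arm effect is the baseline-adjusted difference between arms averaged over the months.*

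Specify the score taken before the first session. The score after the last session must not serve as baseline, because treatment may already have changed it. In the same edit, reconcile the 6-month window in Section 16 with the roughly 8 months given elsewhere for monthly craving; this does not alter the conclusion.

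Cost: a short insertion, with no new visits or data. The downside is one or a few model degrees of freedom, under 1 point of power if baseline craving turns out to be unrelated to follow-up.

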## **17. Confidentiality**

1. Data Security: Trained research staff will be instructed to keep the content of the records confidential. During the initial consent process subjects will be told that they have the right to refuse to answer questions; however, this may affect whether they continue in the study. At all points in the study subjects will be warned at the beginning of procedures which involve the disclosure of personal and sensitive information. These warnings will occur in the introductory comments of interviews or in the instructions of questionnaires and surveys.

Only research staff will have access to subject information. Data contained on paper records and computer files will not include names or other identifying information of subjects. Records containing identifying information will be stored in a private research office in a locked file cabinet and be accessible only by the principal investigator and staff. The study

coordinator or the principal investigator will review and remind research staff of this guideline on a regular basis. Paper and electronic records will be kept for 3 years or longer. Paper records not under use will be stored in locked file cabinets in a private research space. Any identifying information on magnetic or optical media will be stored in a similar manner or be password protected. The password for accessing this information will be available to only select staff that need access to the information to conduct their research duties. All other data will not contain identifying information. All other data will be stored on encrypted magnetic or optical media that is secured or on computer systems accessible only by research staff and computer system administrators via password.

***No copy of the consent form or other research study information will be placed in the participants' medical, employment, or educational records.***

1. Optional Unencrypted Digital Communication With Participants: Participants have the option to provide informed consent for the study team to contact them using unencrypted email and/or unencrypted text message. This communication would primarily be used for appointment scheduling purposes. Souvenir MRI screenshots will not be sent using unencrypted communication means.

## **18. Provisions to Monitor the Data to Ensure the Safety of Participants**

*N/A*

## **19. Provisions to Protect the Privacy Interests of Participants**

1. Protecting Privacy: Only research staff will have access to subject information. Data contained on paper records and computer files will not include names or other identifying information of subjects. Records containing identifying information will be stored in a private research office in a locked file cabinet and be accessible only by the principal investigator and the study coordinator. The study coordinator or the principal investigator will review and remind research staff of this guideline on a regular basis. Paper and electronic records will be kept for 3 years or longer. Paper records not under use will be stored in locked file cabinets in a private research space. Any identifying information on magnetic or optical media will be stored in a similar manner or be password protected. The password for accessing this information will be available to only select staff that need

access to the information to conduct their research duties. All other data will not contain identifying information. All other data will be stored on encrypted magnetic or optical media that is secured or on computer systems accessible only by research staff and computer system administrators via password.

2. As part of study interviews, questions may be asked which touch on sensitive or private issues which the subject may feel uncomfortable discussing. Although there is a potential for disclosure of sensitive personal information, every effort will be made to lessen the risk. The subject may refuse to answer any questions they do not wish to answer at any time; however, this may lead to their discontinuation from the study protocol.
3. Access to Participants: Research team will not access any medical records from participants.

#### **1. Compensation for Research-Related Injury**

1. Compensation for Research-Related Injury: There is no compensation in the event of research-related injury. The consent form states: "In the event that this research activity results in an injury, treatment will be available, including first aid, emergency treatment and follow-up care as needed. Care for such injuries will be billed in the ordinary manner, to you or the participant's insurance company. If you think that you have suffered a research-related injury, please let us know right away."
2. Contract Language: N/A

#### **21.0 In Case of Acute Mental Health**

1. If a participant endorses thoughts of suicide (SCID-IV screening), the action(s) taken will depend on the level of risk.

For low risk, research staff will encourage the participant to speak with their treatment program (e.g. Lodging Plus) therapist and give an IRB approved resource card with the following information:

- Thoughts of suicide: National Suicide Prevention Lifeline, [name]
- Feeling like a threat to yourself or others: 911
- Addiction and mental health services referral: Substance Abuse and Mental Health Services Administration, [name]

For medium risk, research staff will consult with the PI and/or the study clinicians prior to the participant leaving the appointment to determine best steps to take. Recommended steps include continued monitoring, encouraging use of the suicide hotline as needed, and consulting the participant's therapist.

For high risk, research staff will immediately alert the PI and/or study clinicians to ensure proper steps are taken. Research staff will inform treatment staff (e.g. Lodging Plus) directly. If neither is available, research staff will bring the participant to the Fairview-Riverside UMMC Emergency Department for care.

2. If a participant is suffering from active and/or unstable Axis I disorders, suicidal ideation, and/or homicidal ideation mid-study, their participation will be discontinued.

## **1. Consent Process**

1. Consent Process (when consent will be obtained): Consent will take place either in a private room in the Ambulatory Research Center housed in the Department of Psychiatry at the University of Minnesota (in person) or in a private research-designated area within the Lodging Plus addiction treatment program (remotely). Depending on location, consent will be completed in person or remotely (through a video conference). If consent is completed remotely, an eConsent form will be completed in RedCap while using Zoom or a phone call.

**COVID-19 Adaptations:** The following modifications to consent procedures may be used to mitigate pandemic-related risks while participating in this study. These modifications may stay in place even after the pandemic-related risks are considered to have diminished:

- Consent procedures will be completed remotely using REDCap, while also using Zoom or a phone call to communicate to the participant who will be in a private research-designated area within the Lodging Plus addiction treatment program. The physical consent form will be available to the participant at the Lodging Plus addiction treatment program and then a copy with all required emailed to them.
- The electronic versions of forms in REDCap may be formatted slightly different than the paper versions, due to limited formatting options in REDCap. The content will be the same.

The study research staff will thoroughly describe the study and read the consent form. Then the patient will be given time to read the consent form and ask questions of study staff. If the patient agrees, they will sign the consent with the study staff person looking on. Part of the consent involves asking questions of the patient and having him or her record their responses in the Assessment of Informed Consent form to ensure they understand the study and that they can terminate participation at any point. To **protect vulnerable populations**, if the patient does not seem to fully understand the nature of the study (including procedures, risks, confidentiality, voluntary nature), they will not be included in the study. They are also informed that study staff may terminate study participation at any point if they are concerned about the patient's welfare or behavior.

2. To ensure ongoing consent: After consent is provided and at each intervention day, participants are monitored for any concerns they have about the intervention with the Treatment Side Effect Questionnaire. Participants who agree to continue in the study will sign this questionnaire daily.
3. Waiver or Alteration of Consent Process (when consent will not be obtained): N/A
4. Non-English Speaking Participants: We will not enroll participants who do not speak English.
5. Participants Who Are Not Yet Adults (infants, children, teenagers under 18 years of age): We will not recruit participants under 18 years of age.
6. Cognitively Impaired Adults, or adults with fluctuating or diminished capacity to consent: We will record the informed consent process in the "Documentation of the Informed Consent Process" to ensure full understanding of study procedures and voluntary nature. In addition to the informed consent assessment, participants will complete the Montreal Cognitive Assessment (MoCA), which has been modified to be administered remotely (Blind – Version 8.1). This will be administered at the baseline visit after Informed Consent. If a participant has a score of 14 or below (out of 22 possible points), they will not be included in the study because of potential cognitive impairment.
7. Adults Unable to Consent: We will not recruit any individual unable to consent for themselves.

